APPENDIX A LABORATORY ASSAYS

Specific antibody measurements:

Anti-gE ELISA: Anti-gE antibody concentrations will be measured using an anti-gE ELISA. Diluted blood serum samples of study subjects will be added to microtiter wells pre-coated with gE antigen. Secondary peroxidase-conjugated anti-human Abs will be added, which bind to the primary human anti-gE Abs. After incubation of the microtiter wells with a chromogen substrate solution, the enzymatic reaction will be stopped. Optical densities will be recorded and anti-gE antibody concentrations are calculated from a standard curve. The assay cut-off is 97 mIU/mL. ~~The assay will be performed on human serum at GSK Biologicals' laboratory or another laboratory designated by GSK Biologicals.~~

CRDL Clinical Research and Development Lead

CRF Case Report Form

CSR Clinical Study Report

CTRS Clinical Trial Registry Summary

EL.U/ml ELISA unit per milliliter

Eli Type Internal GSK database code for type of elimination code

ELISA Enzyme-linked immunosorbent assay

EoS End of Study

ES Exposed Set (formally called 'Total Vaccinated Cohort')

GMC Geometric mean antibody concentration

GMT Geometric mean antibody titre

GSK GlaxoSmithKline

IU/ml International units per milliliter

LL Lower Limit of the confidence interval

LLOQ Lower Limit of Quantification

204487 (ZOSTER-059 PRI) Statistical Analysis Plan Amendment 3

MedDRA Medical Dictionary for Regulatory Activities

MGI Mean Geometric Increase

MOPA Multiplex Opsonophagocytosis Assay

PCD Primary Completion Date

PD Protocol Deviation

PDMP Protocol Deviation Management Plan

PPS Per-Protocol Set (formally called 'According to Protocol')

PT Preferred Term

SAE Serious adverse event

SAP Statistical Analysis Plan

SBIR GSK Internet Randomization System

SD Standard Deviation

SHS Study Headline Summary

SOC System Organ Class

SUSAR Suspected Unexpected Serious Adverse Reactions

TFL Tables Figures and Listings

TOC Table of Content

UL Upper Limit of the confidence interval

ULOQ Upper Limit of Quantification

VRR Vaccine response rate

YOA Years of Age

204487 (ZOSTER-059 PRI) Statistical Analysis Plan Amendment 3

1. DOCUMENT HISTORY

Date	Description	Protocol
		Version
13 APR	First Version	Amendment 2:
2018		30 JAN 2018
11 JUN	Amendment 1 - Summary of changes as below:	Amendment 2:
2019	- As per new process applicable, the front page has been	30 JAN 2018
	modified to remove the names of all the contributing author	
	and reviewers. Also, sign-off is only required to be done by	
	Lead Statistician	
	- Updated LLOQ and newly calculated ULOQ for the 13	
	pneumococcal serotypes tested by MOPA have been added	
	and accordingly analysis of immunogenicity section has been	
	updated.	
	- Consort table have been added for subject disposition.	
	- Additional tables for fatal serious adverse events (SAEs) and	
	grade 3 non-serious unsolicited adverse events (AEs) have	
	been added.	
	- The term "symptom" has been changed to "adverse event	
	(AE)" in endpoints, table titles and content for solicited AEs,	
	unsolicited AEs, SAEs, and potential immune mediated	
	diseases (pIMDs).	
	- Table 'Summary of temperature value by half degree	
	increment reported during the 7-day (Days 1-7) post-	
	vaccination following each dose' has been removed	
	- Sequence of analysis has been updated	
	- Inclusion of Enrolled and Randomized Set definition	
	- Code 1500 in elimination codes has been removed and added	
	under code 1070. Also, mandatory columns have been added	
	in the elimination table under 'Elimination from PPS section.	
20-	Amendment 2 - Summary of changes as below:	Amendment 2:
NOV-	- The active phase analysis has been removed as a request for	30 JAN 2018
2019	a CTRS posting extension has been submitted to NIH;	
	complete CTRS posting will be done at Last Subject Last Visit	
	(LSLV) + 12 months rather than Primary Completion Date	
	(PCD) +12 months as previously planned	
	- Titles and Footnotes of selected templates have been updated	
	following the Dry run kick-off meeting	
	- Two new safety templates have been added (Templates 49	
	and 50)	
23-	Amendment 3 – Summary of changes: -	Amendment
NOV-	Few templates have been edited for better presentation	2: 30 JAN
2020	Removal of template for vaccine response table with only one	2018
	group for primary objective assessment; Addition of separate	
	template for anti-gE seropositivity rate and GMC, list of PT	
	codes to identify suspected HZ episode	

204487 (ZOSTER-059 PRI) Statistical Analysis Plan Amendment 3

2. STUDY DESIGN

Figure 1 Overview of Study Design

Vacc: vaccination; BS: blood sample; Pre-Vacc: pre-vaccination; FU: follow-up

Experimental design: Phase IIIB, open-label, randomized, controlled, multi-centric, and multi-country, with two parallel groups.

Duration of the study: The intended duration of the study per subject is approximately 14 months for subjects from the Co-Ad group and approximately 16 months for subjects from the Control group.

• Epoch 001: Primary starting at Visit Day 1 and ending with the phone contact at Month 16.

Primary completion date (PCD): Visit Month 5.

End of Study (EoS): Last testing results released of samples collected at Visit Month 3 (Co-Ad group) or at Visit Month 5 (Control group).

204487 (ZOSTER-059 PRI) Statistical Analysis Plan Amendment 3

Study groups:

Table 1 Study groups and epochs foreseen in the study

Study groups	Number of subjects	Age	Epochs Epoch 001
Co-Ad	456	≥ 50 years	Х
Control	456	≥ 50 years	Х

Table 2 Study groups and treatment foreseen in the study

Treatment name	Vaccine/Product name	Study	Groups
		Co-Ad	Control
HZ/su	VZV gE	Х	Х
	AS01B	Х	Х
Prevenar13	Prevenar 13	Х	х

Control: active control.

Vaccination schedule(s):

- Co-Ad Group:
 - at Visit Day 1: first dose of HZ/su and one dose of Prevenar13,
 - at Visit Month 2: second dose of HZ/su.
- Control Group:
 - at Visit Day 1: one dose of *Prevenar13*,
 - at Visit Month 2: first dose of HZ/su,
 - at Visit Month 4: second dose of HZ/su.

Treatment allocation: Subjects to be randomized in a 1:1 ratio at Visit Day 1 to either Co-Ad or Control group. Subjects in each group will be stratified by age with the following approximate distribution (not less than 25% in each age strata):

- 171 subjects in the 50-59 Years of Age (YOA) stratum,
- 171 subjects in the 60-69 YOA stratum, and
- 114 subjects in the \geq 70 YOA stratum.

Blinding: open-label.

Table 3 Blinding of study epochs

Study Epochs		Blinding	
Ī	Epoch 001	open	

204487 (ZOSTER-059 PRI) Statistical Analysis Plan Amendment 3

3. OBJECTIVES

3.1. Co-Primary objectives

To determine the vaccine response rate (VRR) to HZ/su (based on humoral immune response) one month after the second vaccine dose, when the first dose of HZ/su is co-administered with *Prevenar13* (Co-Ad group).

Criterion to be used:

The objective is met if the lower limit (LL) of the 95% CI of the VRR for anti-gE antibody concentrations in the Co-Ad group one month after the second vaccine dose is $\geq 60\%$.

If the above objective is met in the Co-Ad group, then the following objective will be evaluated:

To demonstrate non-inferiority of the humoral immune response to two doses of HZ/su at one month after the last vaccine dose, when the first dose of HZ/su is co-administered with *Prevenar13* (Co-Ad group) compared to when two doses of HZ/su are administered subsequent to *Prevenar13* (Control Group).

Criterion for non-inferiority:

One month after the last vaccine dose in each study group, the upper limit (UL) of the 95% confidence interval (CI) for the anti-gE antibodies Geometric Mean Concentration (GMC) ratio between the Control group and the Co-Ad group is <1.5.

If the above non-inferiority objective is met, then the following objective will be evaluated:

To demonstrate non-inferiority of the humoral immune response to *Prevenar13* at one month after the vaccine dose, when *Prevenar13* is co-administered with the first HZ/su dose (Co-Ad group) compared to when *Prevenar13* is administered separately from HZ/su (Control group), for the 13 serotypes included in *Prevenar13* analyzed sequentially.

Criterion for non-inferiority:

One month after the Prevenar13 vaccine dose in each study group, the UL of the 95% CI for each individual pneumococcal conjugate serotype Geometric Mean Titer (GMT) ratio of the Control group over the Co-Ad group is <2.

For the co-primary objectives, fixed sequence testing which allows for full alpha propagation in pre-ordered hypotheses families will be used (see section 6.3.2.1).

3.2. Secondary objective

To evaluate the safety and reactogenicity following administration of HZ/su and *Prevenar13* vaccines, up to one month post last vaccination and during the whole follow-up period, in the Control group and the Co-Ad group.

204487 (ZOSTER-059 PRI) Statistical Analysis Plan Amendment 3

4. ENDPOINTS

4.1. Primary endpoints

HZ/su immunogenicity:

- Vaccine response for anti-gE humoral immunogenicity, as determined by ELISA, in subjects from the Co-Ad group at one month post-dose 2, at Visit Month 3.
- Anti-gE antibody concentrations as determined by ELISA at one month post-dose 2, at Visit Month 3 for the Co-Ad group and Visit Month 5 for the Control group.

Pneumococcal vaccine immunogenicity:

• Anti-pneumococcal antibody titers for the 13 following serotypes as determined by MOPA at one month post-dose at Visit Month 1: 1, 3, 4, 5, 6A, 6B, 7F, 9V, 14, 18C, 19A, 19F, and 23F.

The criteria used to define the VRR is given in Section 12.1.2.

4.2. Secondary endpoints

Occurrence of solicited local and general adverse events:

- Occurrence, duration and intensity of each solicited local adverse event within 7 days (Days 1 7) after each vaccination,
- Occurrence, duration, intensity and relationship to vaccination of each solicited general adverse event within 7 days (Days 1 7) after each vaccination.

Occurrence of unsolicited AEs:

Occurrence, intensity and relationship to vaccination of unsolicited AEs within 30 days (Days 1 - 30) after each vaccination, according to the Medical Dictionary for Regulatory Activities (MedDRA) classification.

Occurrence of SAEs:

- Occurrence and relationship to vaccination of all SAEs from first vaccination at Day 1 up to 30 days post last vaccination.
- Occurrence and relationship to vaccination of all SAEs during the period starting after 30 days post last vaccination up to study end.

Occurrence of pIMDs:

- Occurrence and relationship to vaccination of any pIMDs from first vaccination at Day 1 up to 30 days post last vaccination.
- Occurrence of any pIMDs during the period starting after 30 days post last vaccination up to study end.

204487 (ZOSTER-059 PRI) Statistical Analysis Plan Amendment 3

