6.4. Analysis of safety

6.4.1. Analysis of safety planned in the protocol

The analysis for safety will be based on the Exposed set. All safety analyses may also be performed by age strata (50-59, 60-69 and \geq 70 YOA), if deemed necessary.

When appropriate, tabulations will be presented overall and by time of occurrence relative to last vaccination (e.g. using windows such as Days 1 to 7, Days 1 to 30 and more than 30 days post-vaccination).

The results for the analysis of safety will be tabulated as follows:

- The number and percentage of subjects with at least one local solicited AE, with at least one general solicited AE, and with any solicited AE during the 7-day follow-up period with exact 95% CIs after each vaccine dose and overall by vaccination group will be provided;
- The percentage of subjects reporting each individual solicited local and general AE during the solicited 7-day follow-up period will be tabulated with exact 95% CI;
- For all solicited adverse events, the same tabulation will be performed for grade 3 solicited AEs and for solicited general AEs with relationship to vaccination;
- Number of days with each individual solicited local and general AE during the solicited 7-day follow-up period;
- The proportion of subjects with at least one report of unsolicited AE (containing both serious and non-serious unsolicited AEs) classified by the MedDRA Primary System Organ Class (SOC) and Preferred Terms (PTs) and reported up to 30 days after each vaccination will be tabulated with exact 95% CI;
- The same tabulation will be performed for grade 3 unsolicited AEs and for unsolicited AEs with a relationship to vaccination reported up to 30 days after each vaccination with exact 95% CI. The proportion of AEs resulting in a medically attended visit will also be tabulated;
- Total number/percentages of doses (per dose and overall) followed by AEs will be tabulated:
- Number of subjects with pIMDs will be tabulated;
- SAEs, including fatalities and withdrawal due to AE(s) will be described in detail.

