- Number and percentage of subjects with at least one report of a grade 3 non-serious unsolicited AE during the 30-day (Days 0-29) follow-up period after each vaccination classified according to the MedDRA Primary SOC and PTs will be tabulated, with exact 95% CI. The same will be generated for grade 3 non-serious unsolicited AE considered related to vaccination.
- Number and percentage of subjects with fatal SAEs, classified by MedDRA
 Primary SOC and PTs will be presented with exact 95% CI in two ways:
- With onset of fatal SAE during the period starting from first vaccination to 30 days post last vaccination dose, after 30 days post last vaccination dose to study end and from first vaccination to study end.

204487 (ZOSTER-059 PRI) Statistical Analysis Plan Amendment 3

- Who died during the period starting from first vaccination to 30 days post last vaccination dose, after 30 days post last vaccination dose to study end and entire study period.
- The listing of all subjects who died during the entire study period and their fatal SAEs in the Enrolled Set

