12.1.3. Safety

For a given subject and the analysis of solicited adverse event during the 7 day follow-up period after vaccination, missing or non-evaluable measurements will not be replaced. Therefore, the analysis of the solicited adverse events based on the ES will include only vaccinated subjects with documented safety data (i.e., symptom screen completed). More specifically the following rules will be used:

- Subjects who documented the absence of a solicited adverse event after one dose will be considered not having that adverse event after that dose.
- Subjects who documented the presence of a solicited adverse event and fully or
 partially recorded daily measurement over the solicited period will be included in the
 summaries at that dose and classified according to their maximum observed daily
 recording over the solicited period.

204487 (ZOSTER-059 PRI) Statistical Analysis Plan Amendment 3

- Subjects who documented the presence of a solicited adverse event after one dose
 without having recorded any daily measurement will be assigned to the lowest
 intensity category at that dose (i.e., 38°C for fever or grade 1 for other adverse
 events). The subject will only be presented in the subject with adverse event
 experienced and not in specific grade information.
- Doses without adverse event sheets documented will be excluded.

For analysis of unsolicited AEs, such as SAEs or adverse events by MedDRA Primary SOC and PTs term, and for the analysis of concomitant medications, all vaccinated subjects will be considered. Subjects who did not report the event or the concomitant medication will be considered as subjects without the event or the concomitant medication respectively.

Associated dose: The associated dose for an event (e.g., AE, medication, vaccination,...) is the study dose given before an event. In case the event takes place on a day a study dose is given, the associated dose will be that of the study dose even if the event actually took place before. For instance, for a conc. medication started on the day of study dose 2 but before dose 2 administrations, the associated dose will be dose 2

The way the percentage of subjects will be derived will depend on the event analysed (see the following table for details). As a result, the denominator (N) will differ from one table to another.

Event	N used for deriving %	Terminology used in the tables for N
Concomitant	All vaccinated subjects	Number of subjects with at least one

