n/% = number/percentage of subjects reporting the adverse event at least once

204487 (ZOSTER-059 PRI) Statistical Analysis Plan Amendment 3

Template 25 Number (%) of subjects with serious adverse events from <first vaccination dose up to 30 days post last vaccination, 30 days post last vaccination up to study end, first vaccination dose up to <database freeze date(DDMMMYYYY)><study end>, including number of events reported <Exposed Set>

			<ea< th="">ch gro N =	up>	</ea<>	ch gro N =	up>
Type of Event	Primary System Organ Class	Preferred Term (CODE)	n*	n	%
SAE	At least one adverse event				
	<each soc=""></each>	<each pt="" term=""></each>			
Related SAE	At least one adverse event				
	<each soc=""></each>	<each pt="" term=""></each>			
Fatal SAE	At least one adverse event				
	<each soc=""></each>	<each pt="" term=""></each>			
Related fatal SAE	At least one adverse event				
	<each soc=""></each>	<each pt="" term=""></each>			

<each group>:

Co-Ad = Dose 1: Prevenar 13+ HZ/su, Dose 2: HZ/su Control = Dose 1: Prevenar 13, Dose 2: HZ/su, Dose 3: HZ/su

N = number of subjects with the administered dose

n* = number of events reported

n/% = number/percentage of subjects reporting the adverse event at least once

204487 (ZOSTER-059 PRI) Statistical Analysis Plan Amendment 3

Template 26 Number (%) of subjects reported solicited local adverse events during the 7-day (Days 1-7) post-vaccination period following each dose and across dose <Exposed Set>

						Co-A	νd			(Contr	ol 💮	
							95%	6 CI				95%	6 CI
Dose	Adverse event	Product	Туре	N	n	%	LL	UL	N	n	%	LL	UL
Dose 1	Pain	HZ/su	All										
			Grade 2 or 3										
			Grade 3										
			Medical advice										
		Prevenar	All										
			Grade 2 or 3										
			Grade 3										
			Medical advice										
	Redness (mm)	HZ/su	All										
	, ,		>50										
			>100										
		Prevenar	Medical advice										
			All										
			>50										
			>100										
			Medical advice										
	Swelling (mm)	HZ/su	All										
			>50										
			>100										
			Medical advice										
		Prevenar	All										
			>50										
			>100										
			Medical advice										
Dose 2													
Dose 3													
Across dose													

Co-Ad = Dose 1: Prevenar 13+ HZ/su, Dose 2: HZ/su

Control = Dose 1: Prevenar 13, Dose 2: HZ/su, Dose 3: HZ/su

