,	Face injury (10050392)				
	Head injury (10019196)				
Skin and subcutaneous tissue disorders (10040785)	Miliaria (10027627)				

Co-Ad = Dose 1: Prevenar 13+ HZ/su, Dose 2: HZ/su

Control = Dose 1: Prevenar 13, Dose 2: HZ/su, Dose 3: HZ/su

At least one adverse event = at least one adverse event experienced (regardless of the MedDRA Preferred Term) N = number of administered doses

n/% = number/percentage of doses followed by the adverse event

95% CI = exact 95% confidence interval; LL = Lower Limit, UL = Upper Limit

204487 (ZOSTER-059 PRI) Statistical Analysis Plan Amendment 3

Template 41 Number and percentage of subjects reporting the occurrence of <serious adverse events, potential Immune Mediated Disease> classified by MedDRA Primary System Organ Class and Preferred Term from <first vaccination up to 30 days post last vaccination, from 30 days post last vaccination dose up to end of study, from first vaccination up to study end> <,including number of events><Exposed Set>

			(-Ad =			(trol =
				95% CI					95% CI	
Primary System Organ Class (CODE)	Preferred Term (CODE)	n*	n	%	LL	UL	n*	n ^c	% L	L UL
At least one adverse event										
Blood and lymphatic system disorders (10005329)	Leukocytosis (10024378)									
Cardiac disorders (10007541)	Acute myocardial infarction (10000891)									
	Atrial fibrillation (10003658)									
	Cardiac failure congestive									
	(10007559)									
	Tachycardia (10043071)									
	Ventricular tachycardia (10047302)									

Co-Ad = Dose 1: Prevenar 13+ HZ/su, Dose 2: HZ/su

Control = Dose 1: Prevenar 13, Dose 2: HZ/su, Dose 3: HZ/su

At least one adverse event = at least one adverse event experienced (regardless of the MedDRA Preferred Term)

N = number of subjects included in the considered cohort in each group

n/% = number/percentage of subjects reporting the adverse event at least once

n* = **n**umber of events reported

95% CI = exact 95% confidence interval; LL = Lower Limit, UL = Upper Limit

Please note that n* will be used to present pIMD for CTRS posting.

Template 42 Global Summary of <serious adverse events, potential Immune
Mediated Disease> <with causal relationship with vaccination>
reported from <first vaccination up to 30 days post last vaccination,
from 30 days post last vaccination dose up to end of study, from
first vaccination up to study end> <Exposed Set>

	Co-Ad	Control	Total
Number of subjects with at least one <sae, pimd=""> reported</sae,>			

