Co-Ad = Dose 1: Prevenar 13+ HZ/su, Dose 2: HZ/su

Control = Dose 1: Prevenar 13, Dose 2: HZ/su, Dose 3: HZ/su

Note: This graph is provided as an example. The same graph will be provided in colour for each time point and each assay comparing the values of the groups

Please note to consider PRE and PI(M1) for both group for pneumococcal antibody. For gE antibody, PRE and PII(M3) for Co-Ad and PI(M2) and PIII(M5) for Control group.

204487 (ZOSTER-059 PRI) Statistical Analysis Plan Amendment 3

Template 45 Number and percentage of subjects <with><experiencing> fatal SAEs classified by MedDRA Primary System Organ Class and Preferred Term <who died><with onset of fatal SAE> <during the period starting> <from first vaccination up to 30 days post last vaccination dose> <after 30 days post last vaccination dose up to study end><from first vaccination until the study end><during the entire study period> <Exposed Set>

			_	o-A N =				ontr N =	trol =		
				95% CI				ć	95% CI		
Primary System Organ Class (CODE)	Preferred Term (CODE)	n	%	LL	UL	n	%	LL	UL		
At least one adverse event											
Blood and lymphatic system disorders (10005329)	Leukocytosis (10024378)										
Cardiac disorders (10007541)	Acute myocardial infarction (10000891)										
	Atrial fibrillation (10003658)										
	Cardiac failure congestive										
	(10007559)										
	Tachycardia (10043071)										
	Ventricular tachycardia (10047302)										

Co-Ad = Dose 1: Prevenar 13+ HZ/su. Dose 2: HZ/su

Control = Dose 1: Prevenar 13. Dose 2: HZ/su. Dose 3: HZ/su

At least one adverse event = at least one adverse event experienced (regardless of the MedDRA Preferred Term)

N = number of subjects included in the considered cohort in each group

n/% = number/percentage of subjects reporting the adverse event at least once

95% CI = exact 95% confidence interval; LL = Lower Limit, UL = Upper Limit

Template 46 Summary of subject disposition from Enrolled Set to Randomized Set

	Total N=XXX n %
Number of subjects who signed an informed consent	
Withdrawals prior to randomization	XXX XX.X
<withdrawal 1="" reason=""></withdrawal>	xxx xx.x
<withdrawal 2="" reason=""></withdrawal>	xxx xx.x
	xxx xx.x
	xxx xx.x
Number of subjects included in Randomized Set	

N = **n**umber of subjects

n% = number / percentage of subjects in a given category

204487 (ZOSTER-059 PRI) Statistical Analysis Plan Amendment 3

Template 47 Summary of subject disposition from Randomized Set to Per Protocol Set

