Control = Dose 1: Prevenar 13, Dose 2: HZ/su, Dose 3: HZ/su

N = number of subjects included in the considered cohort in each group

n/% = number/percentage of subjects reporting the adverse event at least once 95% CI = exact 95% confidence interval; LL = Lower Limit, UL = Upper Limit

Template 50 Summary of subjects by serious adverse event and potential Immune Mediated Disease categories, with onset <from first vaccination to 30 days post last vaccination, after 30 days post last vaccination until study end>

			•		iroup 2		>	
	N=X	XXX		N=XXXX				
		95%	6 CI			95% CI		
n	%	LL	UL	n	%	LL	UL	
XXX	xx.x	XX.X	XX.X	XXX	XX.X	XX.X	XX.X	
XXX	xx.x	xx.x	xx.x	XXX	XX.X	xx.x	xx.x	
XXX	XX.X	XX.X	XX.X	XXX	XX.X	XX.X	XX.X	
XXX	XX.X	XX.X	XX.X	XXX	xx.x	XX.X	XX.X	
	XXX XXX	n % xxx xx.x xxx xx.x xxx xx.x	n % LL xxx xx.x xx.x xx.x xxx xx.x xx.x x	95% CI	95% CI n % LL UL n xxx xx.x xx.x xx.x xx.x xxx xxx xx.x xx.x xx.x xx.x xxx xxx xx.x xx.x xx.x xx.x xxx	95% CI n % LL UL n % xxx xx.x xx.x xx.x xx.x xx.x xx.x xx	95% CI 95% n % LL UL n % LL xxx xx.x xx.x xx.x xx.x xx.x xx.x x	

Co-Ad = Dose 1: Prevenar 13+ HZ/su, Dose 2: HZ/su

Control = Dose 1: Prevenar 13, Dose 2: HZ/su, Dose 3: HZ/su

N = number of subjects included in the considered cohort in each group

n/% = number/percentage of subjects reporting the adverse event at least once

95% CI = exact 95% confidence interval; LL = Lower Limit, UL = Upper Limit

204487 (ZOSTER-059 PRI) Statistical Analysis Plan Amendment 2

	Statistical Analysis Flatt Americanent 2
GlaxoSmithKline	Statistical Analysis Plan
Detailed Title:	A Phase IIIB, randomized, open-label, multicenter clinical trial to assess the immunogenicity and safety of GSK Biologicals' Herpes Zoster vaccine GSK1437173A when co-administered with Prevenar13 in adults aged 50 years and older.
eTrack study number and Abbreviated Title	204487 (ZOSTER-059 PRI)
Scope:	All analyses planned per protocol.
Date of Statistical Analysis Plan	Amendment 2 Final: 20 November 2019

APP 9000058193 Statistical Analysis Plan Template V4 (Effective date: 3 June 2019)

204487 (ZOSTER-059 PRI) Statistical Analysis Plan Amendment 2

TABLE OF CONTENTS

				PAGE
LIS	T OF A	BBREVIA	ΓΙΟΝS	10
1.	DOCU	JMENT HIS	STORY	12
2.	STUD	Y DESIGN	l	13
3.	OR IE	CTIVES		15
٥.	3.1.		ıry objectives	
	3.2.		ry objective	
4.	ENDF	OINTS		16
	4.1.		endpoints	
	4.2.	Secondar	ry endpoints	16
5.	ANAL	YSIS SETS	3	17
	5.1.			
		5.1.1.	Enrolled Set	
			Randomized Set	
		5.1.3.	Exposed Set (ES)*	

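### First-period percentages of subjects with SAEs, pIMDs and fatal SAEs cover about 90 days in Co-Ad and 150 in Control, with no person-time incidence beside them

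*SAP*

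**What the plan says.** SAP section 4.2 (and protocol 10.2) splits follow-up for SAEs into two periods. The first is "Occurrence and relationship to vaccination of all SAEs from first vaccination at Day 1 up to 30 days post last vaccination"; the second runs from then to study end. pIMDs are split in the same way. For deaths, SAP 6.4.2 repeats the first period: "With onset of fatal SAE during the period starting from first vaccination to 30 days post last vaccination dose".

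The tables for this period, in SAP 13.2, are:

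- Template 25 ("vaccination dose up to 30 days post last vaccination, 30 days post last vaccination up to study end"): subject counts and percentages, with event counts.
- Template 41 ("Number and percentage of subjects reporting the occurrence of <serious adverse events, potential Immune Mediated Disease>"): counts and percentages with exact 95% CIs.
- Template 45 ("fatal SAEs classified by MedDRA Primary System Organ Class and Preferred Term"): the same for deaths.
- Template 50 ("Summary of subjects by serious adverse event and potential Immune Mediated Disease categories"): a summary by period with CIs.

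The SAE denominator in SAP 12.1.3 is all vaccinated subjects, and length of observation plays no part: "Subjects who did not report the event or the concomitant medication will be considered as subjects without the event". SAP 6.4.1 allows tabulations "by time of occurrence relative to last vaccination", but only where appropriate. The only incidence defined is per dose (SAP 12.1.1), and a dose there is a vaccination visit. Neither the protocol nor SAP Amendment 3 plans a person-time or exposure-adjusted incidence.

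**The concern.** The first period is tied to the last dose, and the last dose comes two months later in Control. The longer window gives Control more time to accrue illnesses and deaths that have nothing to do with vaccination. Side by side, the percentages would then make co-administration, the strategy under test, look safer than it is. Under a constant hazard, a true Co-Ad/Control rate ratio of 1.67 would appear as equal percentages.

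This period is half of the secondary objective in SAP 3.2, which asks for safety up to one month after the last vaccination as well as over the whole follow-up. Nothing on the four templates tells the reader how long each group was observed.

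**Working it through.** **Schedule check.** Last dose at Month 2 or Month 4, plus 12 months of follow-up, gives 2 + 12 = 14 and 4 + 12 = 16 months. These match the durations stated in SAP section 2.

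**Length of the first period** (schedule in SAP section 2; allowed intervals in protocol Tables 8 and 9).

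| | Co-Ad | Control |
|---|---|---|
| Nominal | 60 + 30 = 90 days | 60 + 60 + 30 = 150 days |
| Shortest allowed | 49 + 30 = 79 | 60 + 49 + 30 = 139 |
| Longest allowed | 83 + 30 = 113 | 83 + 83 + 30 = 196 |

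The allowed ranges do not overlap. The nominal ratio is 90/150 = 0.60. At opposite extremes of the visit intervals it is 79/196 = 0.40 and 113/139 = 0.81. Those extremes would need every subject in each group at one end of the range, so 0.60 is the informative figure.

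**The second period is balanced.** In both groups it runs from 335 − 30 = 305 to 395 − 30 = 365 days.

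**Direction of the bias.** Let f be the share of Control's events that are background, at an equal constant rate in both groups. The remainder are caused by injections, three in each group. For small risks:

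- ratio of percentages (Co-Ad/Control) = (1 − f) + 0.6f
- ratio of person-time rates = the above × 150/90

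| f | Percentages | Person-time rates |
|---|---|---|
| 0 | 1.00 | 1.67 |
| 0.25 | 0.90 | 1.50 |
| 0.50 | 0.80 | 1.33 |
| 0.75 | 0.70 | 1.17 |
| 1 | 0.60 | 1.00 |

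Each measure is unbiased at one end only.

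**Illustration.** The documents give no SAE rate, so annual risks are assumed, equal in both groups and all background, with 456 subjects per group and no dropout. Risk over d days = 1 − (1 − annual risk)^(d/365.25).

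| Assumed annual risk | Co-Ad | Control | Subjects |
|---|---|---|---|
| 3% | 0.75% | 1.24% | 3 v 6 |
| 6% | 1.51% | 2.51% | 7 v 11 |
| 10% | 2.56% | 4.23% | 12 v 19 |

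At 6% the Clopper-Pearson intervals are 0.6–3.1% and 1.2–4.3%, which overlap. Person-years at full follow-up are 456 × 90/365.25 = 112.4 and 456 × 150/365.25 = 187.3. The same 7 and 11 subjects give 7/112.4 = 6.2 (exact Poisson 95% CI 2.5–12.8) and 11/187.3 = 5.9 (2.9–10.5) per 100 person-years, so the apparent gap disappears.

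**Whole study.** With 60 + 365 = 425 and 120 + 365 = 485 days, the 6% case gives 6.95% v 7.89%, a ratio of about 0.88.

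**Per-dose route.** Template 42 counts doses followed by an SAE or pIMD and Template 14 gives total doses. Over the first period a dose covers 90/2 = 45 days in Co-Ad and 150/3 = 50 in Control, a ratio of 0.90 for background events. This is nearer to balance, but the reader must build it and no CI is planned.

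**The case against.** The best counter-argument is Template 40. It gives the percentage of doses followed by unsolicited AEs within 30 days, with an exact CI and an equal 30-day window per dose in both groups. SAP 6.4.1 says unsolicited AEs include serious ones, so serious events within 30 days of a dose are in that table. This stands as partial mitigation. But Template 40 does not show SAEs, pIMDs or deaths as classes, and it omits days beyond 30 after each dose.

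Other planned outputs also help. The second period is balanced, the whole-study tables are only mildly affected, and Template 36 lists every SAE by dose and day of onset. None of these gives a first-period incidence on time at risk.

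A second objection is that person-time has its own bias, against Co-Ad, when events are injection-caused. Relationship to vaccination is part of the first-period endpoints, and for related events the percentage is the less distorted measure. That is correct, and it is why the percentages should stay.

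A third is that the stakes are modest. Safety is descriptive with no between-group test, SAP section 7 rests the trial's conclusion on the co-primary objectives alone, and events may be few with wide intervals. This limits the weight of the point. It does not remove a systematic difference in observation time that the tables leave unstated.

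**Conclusion.** The concern holds. The first safety period is about two-thirds longer in Control (150 v 90 days nominally), and the planned percentages take no account of it. The distortion is a Co-Ad/Control ratio of about 0.60 if all events are background at an equal constant rate. It shrinks to none if all are injection-caused; the true mix cannot be known from the documents. The window lengths apply to subjects who complete vaccination on schedule, and the percentages and counts in the illustration rest on assumed annual risks. The consequence is confined to interpretation of the secondary safety objective. This is a worthwhile, inexpensive improvement and does not threaten the trial's conclusions.

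**What to change.** In SAP 6.4, keep the planned percentages. Add, for the first period and optionally the whole study, incidence per 100 person-years with 95% CI by group for SAEs, pIMDs and fatal SAEs. Count time from first vaccination to the first event, withdrawal or end of the period.

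On Templates 25, 41, 45 and 50, add a footnote giving the nominal windows of 90 and 150 days. It should say that percentages favour Co-Ad for background events, that person-time rates favour Control for injection-caused events, and that the two should be read together.

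Unsolicited AEs are observed for 2 × 30 = 60 v 3 × 30 = 90 days per subject; a pointer to the per-dose Template 40 is enough there. Leave the second period as it is.

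The cost is one or two tables plus footnotes. Vaccination and contact dates are already in the SAP 13.1 listings and day of onset is in Template 36, so no new data are needed. SAP section 13 lets footnotes be adapted without an amendment; the added rate tables would need a small SAP update.
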